3. STUDY POPULATION

Up to 25 subjects may be enrolled. Subjects must meet all the inclusion criteria and none of the exclusion criteria to receive a treatment assignment.

3.1. Inclusion Criteria

Subjects must meet the following criteria at Screening to be eligible to participate in the study.

1. Be at least 16 years of age;
2. Histologic diagnosis of resected Stages IIIB/IIIC/ IV melanoma, with no evidence of disease clinically and radiologically, and negative surgical margins. All melanomas regardless of primary site of disease will be allowed;
3. Eastern Cooperative Oncology Group (ECOG) performance status score of 0 or 1 (Appendix 2);
4. Prior chemotherapy or immunotherapy (tumor vaccine, cytokine, or growth factor given to control the cancer) must have been completed at least 4 weeks before study drug administration, and all adverse events have either returned to baseline or stabilized;

5. Prior treated brain or meningeal metastases must be without magnetic resonance imaging (MRI) evidence of progression for at least 8 weeks and off immunosuppressive doses of systemic steroids (> 10 mg/day prednisone or equivalent) for at least 2 weeks before study drug administration;
6. Prior systemic radiation therapy must have been completed at least 4 weeks before study drug administration. Prior focal radiotherapy completed at least 2 weeks before study drug administration. No radiopharmaceuticals (strontium, samarium) within 8 weeks before study drug administration;
7. Immunosuppressive doses of systemic medications, such as steroids or absorbed topical steroids (doses > 10 mg/day prednisone or equivalent) must be discontinued at least 2 weeks before study drug administration;
8. Completed nitrosourea treatment at least 6 weeks before administration of any study drug;
9. Prior surgery that required general anesthesia must be completed at least 4 weeks before study drug administration. Surgery requiring local/epidural anesthesia must be completed at least 72 hours before study drug administration and subjects should be recovered;
10. Screening laboratory values must meet the following criteria:
 - white blood cells (WBCs) ≥ 2000 cells/ μ L
 - neutrophils ≥ 1500 cells/ μ L
 - platelets $\geq 100 \times 10^3/\mu$ L
 - hemoglobin ≥ 9.0 g/dL
 - serum creatinine ≤ 2 mg/dL
 - AST ≤ 2.5 x upper limit of normal (ULN) without, and ≤ 5 x ULN with hepatic metastasis
 - ALT ≤ 2.5 x ULN without, and ≤ 5 x ULN with hepatic metastasis
 - bilirubin ≤ 2 x ULN (except subjects with Gilbert's syndrome, who must have total bilirubin < 3.0 mg/dL)

11. Females of childbearing potential must:

use appropriate method(s) of contraception. *WOCBP should use an adequate method to avoid pregnancy for 23 weeks (30 days plus the time required for nivolumab to undergo five half-lives) after the last dose of investigational drug*

Women of childbearing potential must have a negative serum or urine pregnancy test (minimum sensitivity 25 IU/L or equivalent units of HCG) within 24 hours prior to the start of nivolumab

-
12. For female subjects to be considered as not having childbearing potential, they must meet 1 or more of the following criteria:
 - postmenopausal for at least 24 consecutive months;
 - surgically sterile (ie, have had a hysterectomy or bilateral oophorectomy);
 - females with irregular menstrual periods and/or on hormone replacement therapy must have a documented serum follicle stimulating hormone level > 35 mIU/mL;
 13. Men who are sexually active with WOCBP must use any contraceptive method with a failure rate of less than 1% per year *Men receiving nivolumab and who are sexually active with WOCBP will be instructed to adhere to contraception for a period of 31 weeks after the last dose of investigational product Women who are not of childbearing potential (ie, who are postmenopausal or surgically sterile as well as azoospermic men do not require contraception*
 14. Subject must have read, understood, and provided written informed consent and HIPAA authorization after the nature of the study has been fully explained; and
 15. Willing to adhere to the study visit schedule and the prohibitions and restrictions specified in this protocol.

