5.1.6.4. Other

Hepatitis Test

Test for HBV SAg and HCV antibody will be conducted at Visit 1. Results indicating active or chronic infection will result in study exclusion. HCV RNA assay will be carried out if the antibody assay is positive and will determine if a HCV antibody assay is a true positive.

Pregnancy Test

For female subjects of child bearing potential only. Pregnancy Test: WOCBP prior to dosing nivolumab. A serum or urine pregnancy testing is required within 24 hrs of study [treatment] enrollment or randomization, then every 6 weeks. [more frequently if required by local standard]. After discontinuation from nivolumab these should be repeated at approximately 30 days and approximately 70 days [or more frequently if required by local standard]. Pregnancy tests prior to dosing must be negative.

Immunogenicity Testing

Blood will be collected for immunogenicity testing. Sample preparation and storage instructions are provided in Appendix 4.

Immune Safety Assays

Blood samples for measurement of immune safety parameters will be taken at the times indicated on the Time and Events Schedule (Table 1), and the following parameters will be measured:

- Rheumatoid Factor
- Thyroid Stimulating Hormone
- Free T4 level¹
- Adrenocorticotrophic hormone
- C-Reactive Protein
- Antinuclear Antibody

¹ If abnormal, the sample should be analyzed for free T3 and free T4

The following tests may also be performed on selected stored samples. Samples will be stored up to 10 years

- anti-DNA antibody
- anti-phospholipid antibody
- anti-thyroid receptor antibodies
- anti-islet cell antibody
- anti-neutrophil cytoplasm antibody
- anti-thyroglobulin antibody
- anti-thyroid peroxidase

Additional tests and repeat tests to evaluate abnormal endocrine results may be obtained at the Investigator's discretion if deemed clinically significant. This may include follow up with prolactin and a.m. cortisol tests, and may require an endocrine consult.

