6.9. Pregnancy

Sexually active WOCBP must use an effective method of birth control during the course of the study, in a manner such that risk of failure is minimized. Before enrolling WOCBP in this clinical study, the investigator must review the guideline about study participation for WOCBP which can be found in the GCP Manual for Investigators. The topics include the following:

- General Information
- Informed Consent Form
- Pregnancy Prevention Information Sheet
- Drug Interactions with Hormonal Contraceptives
- Contraceptives in Current Use
- Guidelines for the Follow-up of a Reported Pregnancy.

Before study enrollment, WOCBP must be advised of the importance of avoiding pregnancy during study participation and the potential risk factors for an unintentional pregnancy. The subject must sign an informed consent form documenting this discussion.

All WOCBP MUST have a negative pregnancy test within 72 hours before receiving NIVOLUMAB. The minimum sensitivity of the pregnancy test must be 25 IU/L or equivalent units of HCG. If the pregnancy test is positive, the subject must not receive NIVOLUMAB and must not be enrolled in the study.

In addition, all WOCBP should be instructed to contact the investigator immediately if they suspect they might be pregnant (e.g., missed or late menstrual period) at any time during study participation.

If, following initiation of the investigational product, it is subsequently discovered that a study subject is pregnant or may have been pregnant at the time of investigational product exposure, including during at least 6 half-lives after product administration, the investigational product will be permanently discontinued in an appropriate manner (eg, dose tapering if necessary for subject safety). The investigator must immediately notify BMS of this event and record the pregnancy on the Pregnancy Surveillance Form (not an SAE form). Initial information on a pregnancy must be reported immediately to BMS, and the outcome information provided once the outcome is known. Completed Pregnancy Surveillance Forms must be forwarded to BMS according to SAE reporting procedures.

Any pregnancy that occurs in a female partner of a male study participant should be reported to the Sponsor-investigator. Information on this pregnancy will be collected on the Pregnancy Surveillance Form.

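### Read literally, item 12 of the inclusion criteria lets a single FSH above 35 mIU/mL class a woman with ongoing irregular periods as not of childbearing potential

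*Combined protocol and SAP*

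**What the plan says.** Section 3.1, item 12 defines who is not of childbearing potential. Its opening clause states that "they must meet 1 or more of the following criteria". Three lines follow at the same level:

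- "postmenopausal for at least 24 consecutive months";
- surgical sterility, through removal of the uterus or of both ovaries;
- "females with irregular menstrual periods and/or on hormone replacement therapy must have a documented serum follicle stimulating hormone level > 35 mIU/mL".

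Item 13 describes the exempt group in different terms: "Women who are not of childbearing potential (ie, who are postmenopausal or surgically sterile". It mentions neither FSH nor a 24-month period.

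Several duties depend on the classification:

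- Item 11, contraception: "WOCBP should use an adequate method to avoid pregnancy for 23 weeks" after the last dose.
- Item 11, testing: "Women of childbearing potential must have a negative serum or urine pregnancy test" before nivolumab starts.
- Section 6.9: "Sexually active WOCBP must use an effective method of birth control during the course of the study".
- Section 5.1.6.4 sets pregnancy tests at entry, every 6 weeks, and about 30 and 70 days after nivolumab stops, and opens with "For female subjects of child bearing potential only".

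None of these sections redefines the class.

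**The concern.** The third line of item 12 is phrased as a requirement on a group of women (they must have a certain FSH level), whereas the other two describe a qualifying state. That suggests the FSH value was meant to confirm menopause where the bleeding history is unclear. The opening clause makes it sufficient alone. It asks for no repeat test, no period without menses and no minimum age, in a trial open from age 16.

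A site that applies the text as written could therefore exempt a woman who is still menstruating. What is at stake is pregnancy prevention during exposure to two antibodies. Section 6.9 requires treatment to stop and the company to be notified when a subject is found to be pregnant, and section 6.7 requires every pregnancy to be reported. Those duties act after the event and do not prevent exposure.

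**Working it through.** **Step 1: the logic of item 12.** Take a woman with ongoing irregular periods and one documented FSH above 35 mIU/mL.

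| Line of item 12 | Met? |
|---|---|
| Postmenopausal for 24 consecutive months or more | No |
| Surgically sterile | No |
| Irregular periods and/or hormone replacement therapy, with FSH > 35 mIU/mL | Yes |

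One line met satisfies the opening clause, so she is classed as not of childbearing potential.

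**Step 2: comparison with the neighbouring text.** The first line demands 24 consecutive months; the third accepts continuing menses plus one laboratory value. Item 13 describes exempt women as postmenopausal or surgically sterile, and a woman who is still having periods does not fit that description in its ordinary sense.

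**Step 3: which duties fall away.** Contraception (item 11, section 6.9) and the repeat tests (section 5.1.6.4) are each tied to childbearing potential. Once item 12 takes her out of that class, they no longer attach.

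**Step 4: how long the contraception duty would have lasted.** Inputs: the fourth combination dose is on Day 64 (Table 1); flat dosing starts 4 weeks after it (section 4.2.1.4); dosing is then every 4 weeks for 48 weeks, taken here as 48 / 4 = 12 doses; contraception continues for 23 weeks after the last dose (item 11).

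- Fourth combination dose: (64 − 1) / 7 = 9 weeks after the first dose.
- First flat dose: 9 + 4 = 13 weeks.
- Twelfth flat dose: 13 + 11 × 4 = 57 weeks.
- End of the duty: 57 + 23 = 80 weeks.
- Shortest case, one dose only: 0 + 23 = 23 weeks.

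Using the synopsis's expected maximum treatment duration of 60 weeks instead gives 60 + 23 = 83 weeks. Neither 80 nor 83 is a ceiling: section 4.2.1.2 moves later doses back after a delay, and section 4.2.1.3 allows interruptions of more than 6 weeks after consultation with the medical monitor.

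**Step 5: how many women.** Section 3 caps enrollment at 25 subjects of both sexes. The documents do not say how many women would have irregular periods and a raised FSH; the number may be zero.

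**The case against.** Five counter-arguments deserve weight.

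- **A list of alternatives always admits people who fail the other lines.** A surgically sterile woman need not be 24 months postmenopausal either, and that is no defect. This is fair. Without a premise about fertility, the text shows only that the third route is out of step with the protocol's other standards. A reader might go further and infer that women with an FSH above 35 mIU/mL who still menstruate can conceive, so that the plan exposes fertile women. The documents give no information on that, and the point does not depend on it.
- **Items 12 and 13 can be partly reconciled.** Item 13 sets no duration for postmenopausal, so FSH could be read as the laboratory route to that status. This stands to a degree: it is too strong to call the two items a flat contradiction. The reconciliation works for a woman whose bleeding history is masked by hormone replacement therapy. It is strained for one with continuing periods of her own.
- **Item 13 is the only text that expressly waives contraception, and it may not waive it for her.** True, but the duty in item 11 and section 6.9 attaches only to women of childbearing potential. Once item 12 removes her from that class, no waiver is needed.
- **Other safeguards remain.** Table 1 footnote 4 requires a negative pregnancy test before any study drug and does not limit this to women of childbearing potential; section 5.1.6.4 does. A reader might infer that an exempted woman would have no pregnancy test at all, and the footnote leaves that unsettled. Exclusion 9 bars pregnant or nursing women whatever their classification. Neither provision imposes contraception, and neither clearly restores the 6-weekly and post-treatment tests.
- **A guideline outside the protocol may help.** Section 6.9 refers investigators to a manual on participation of women of childbearing potential. Its content is not in the documents, and the topics listed do not include a definition of the class.

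**Conclusion.** The concern holds as a fault in a safety definition. Followed as written, item 12 removes a woman with ongoing irregular periods from the class that triggers contraception and repeat pregnancy testing, on the strength of one FSH value. This departs from the 24-month line and sits badly with item 13.

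Per woman, the contraception period lost runs from 23 weeks after a single dose to about 80 weeks on the full planned schedule, and longer with delays. These are protocol durations, not estimates of risk. They assume that sites apply the literal wording and, for the 80 weeks, that the 48-week phase consists of 12 doses given on time.

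Few women or none may be affected, and no endpoint, analysis or stopping rule changes. The protocol should still be corrected, because the rule governs fetal exposure and the correction is cheap.

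**What to change.** Replace the three lines of item 12 with wording such as:

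> A woman is not of childbearing potential if (a) she has been postmenopausal for 24 or more consecutive months; or (b) hormone replacement therapy makes her bleeding history uninformative and a documented serum FSH above 35 mIU/mL confirms that she is postmenopausal; or (c) she has had a hysterectomy or bilateral oophorectomy. A woman with ongoing irregular periods not attributable to hormone replacement therapy is of childbearing potential unless (c) applies.

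In item 13, replace the bracketed description of exempt women with a reference to item 12.

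Route (b) is kept on purpose. Requiring 24 months of every woman on hormone replacement therapy would not work where that period cannot be established.

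The change needs a protocol amendment, but it is confined to wording. Its only burden falls on any woman reclassified, who must use contraception during treatment and for 23 weeks after the last dose and have the routine pregnancy tests.

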3.2. Exclusion Criteria

Subjects who fulfill any of the following conditions at Screening will not be eligible for admission into the study:

1. History of severe hypersensitivity reactions to other mAbs;
2. Prior non-melanoma malignancy active within the previous 2 years except for locally curable cancers that have been apparently cured, such as basal or squamous cell skin cancer, superficial bladder cancer, or carcinoma in situ of the prostate, cervix or breast;
3. Subjects with any active autoimmune disease (Appendix 3) or a documented history of autoimmune disease, or history of syndrome that required systemic steroids or immunosuppressive medications, except for subjects with vitiligo or resolved childhood asthma/atopy;
4. Known history of testing positive for human immunodeficiency virus (HIV) or known acquired immunodeficiency syndrome (AIDS);
5. Positive tests for hepatitis B virus surface antigen (HBV SAg) or hepatitis C virus ribonucleic acid (HCV RNA) indicating active or chronic infection;
6. Prior therapy with an anti-PD-1, anti-PD-L1, anti-PDL-2, or anti-CTLA-4 antibody (or any other antibody targeting T cell co-stimulation pathways);
7. Concurrent medical condition requiring the use of immunosuppressive medications, or immunosuppressive doses of systemic or absorbable topical corticosteroids;

8. Underlying medical condition (eg, a condition associated with diarrhea) that, in the Investigator's opinion, would make the administration of either study drug or both study drugs hazardous to the subject or obscure the interpretation of toxicity determination or adverse events;
9. Pregnant or nursing; or
10. Current participation in another clinical study involving treatment with medications, radiation or surgery, or prior participation in this study.
11. Patients are excluded if they have active brain metastases or leptomeningeal metastases. Subjects with brain metastases are eligible if metastases have been treated and there is no magnetic resonance imaging (MRI) evidence of progression for [lowest minimum is 4 weeks or more] after treatment is complete and within 28 days prior to the first dose of nivolumab administration. There must also be no requirement for immunosuppressive doses of systemic corticosteroids (> 10 mg/day prednisone equivalents) for at least 2 weeks prior to study drug administration.
12. As there is potential for hepatic toxicity with nivolumab or nivolumab/ipilimumab combinations, drugs with a predisposition to hepatotoxicity should be used with caution in patients treated with nivolumab-containing regimen.
13. Allergies and Adverse Drug Reaction
 - a. History of allergy to study drug components
 - b. History of severe hypersensitivity reaction to any monoclonal antibody

3.3. Inclusion of Women and Minorities

Both males and females of all races and ethnic groups are eligible for this trial.

3.4. Subject Recruitment and Screening

The patients who are eligible for this research study come directly from the study investigators' clinical patient population. Thus, the investigators are very familiar with their patients' disease status and potential eligibility given the protocol's inclusion and exclusion criteria. All efforts will be made to actively recruit and retain women and members of minority groups in this study. The investigator will approach eligible potential subjects and explain the study in a private room, including the reasons why subjects will be eligible, risks, benefits, and the regimes to be evaluated. The subjects will be given a chance to ask questions to the person consenting him/her and will be able to take the consent home to discuss it with family/friends prior to signing. If the subject agrees s/he will sign the consent form either at the first contact (if the investigator/delegate is convinced that the subject understands) or at the time of a return visit after having had time to study the consent in more depth. Study procedures will not begin until after the consent form has been properly obtained. The subject is entitled to decide not to participate in the trial, without affecting their right to other medical care, and may discontinue participation in the trial at any time without penalty or loss of benefits to which they are entitled.

3.4.1 Informed Consent

Consent will be obtained only by an investigator who has completed requisite training for human subject research and has been instructed by the Principal investigator about the research study and consent process.

The Investigator, or designee, will explain to each subject (or legally authorized representative) the nature of the research study, its purpose, the procedures involved, the expected duration of subject participation, alternative treatment, the potential risks and benefits involved and any discomfort which may occur during the subject's participation in the study. The Investigator will review the informed consent form with patients and address any questions or concerns prior to obtaining written informed consent for participation. Each subject will be informed that participation in the study is voluntary and that he/she may withdraw from the study at any time and that withdrawal of consent will not affect his/her subsequent medical treatment or relationship with the treating physician. For patients ages 16-17, parents will sign the informed consent, and children will sign an Assent, which will accompany the Consent Form. Children who turn 18 during the course of their participation will be approached to go through the full consenting process and be asked to provide written informed consent in order to continue participation.

For non-English speaking patients, institutional translation services will be utilized. For these patients the consent letter and all other information will be administered orally and a witness, not related to the research project, will be present while the oral presentation is given. A short form will be utilized for the subject to sign in his/her name and the translator and/or witness must sign the short form. The translator will also sign the main consent form.

For patients who cannot read. A witness, not related to the research study will be present. The consent will be read to the patient. The patient will also be allowed to ask any questions s/he may have. The investigator will ask the patient questions to ensure s/he understands the study. If the investigator determines the subject understands the study, the patient will mark an X where his/her name would go and the witness will sign the consent form.

This informed consent should be given by means of a standard written statement, written in non-technical language. The subject should read and consider the statement before signing and dating it. The subject will be given a copy of the signed document. The original signed consent document will be retained by the Investigator. If written consent is not possible, oral consent can be obtained if witnessed by a signed statement from 1 or more persons not involved in the study, attesting to the accuracy of the presentation, the apparent understanding of the subject and documenting why the subject was unable to read and sign the form. No subject can enter the study and no study-related procedures can be performed before his/her informed consent has been obtained.

The ICF (that complies with regulatory requirements and is considered appropriate for the study) must be submitted by the Investigator with the protocol for IRB approval.

